4.4.3 Sensitivity Analyses

Due to potentially skewed distribution of the biomarker endpoints, a sensitivity analysis using the non-parametric Mann-Whitney test may be performed as appropriate.

For each of the primary endpoints and exploratory endpoints listed below, an ANCOVA model adjusting for baseline DMT status, baseline biomarker level and other covariates, such as baseline Gd+ T1 lesions category (0, 1, >1) and age, may be conducted, providing sufficient sample size in each covariate category:

- CSF NfL, CD19+ B cell and CD3+T cell
- Blood NfL, CD19+ B cell and CD3+T cell

4.4.4 Subgroup Analyses

The primary efficacy endpoints (change in levels of NfL in CSF, change in number of CD19 + B cells and change in number of CD3 + T cells in CSF) will be further summarized for DMT-naïve and DMT-experienced patients separately, and for patients who experienced at least one relapse during the study and patients experienced no relapse separately.

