4.5.6 Neurological Examinations

Neurological examinations will be performed *at timepoints according to the appropriate schedule of activities* and in the case of relapse or early termination so that the investigator can assess whether the patient is experiencing a relapse of MS or another neurological (non-MS) disorder.

Investigators will also screen patients for signs and symptoms of worsening neurologic function localized to the cerebral cortex, such as cortical symptoms/signs, behavioral and neuropsychological alteration, retrochiasmal visual defects, hemiparesis, cerebellar symptoms/signs (e.g., gait abnormalities, limb incoordination).

Patients with suspected PML should be withheld from ocrelizumab treatment until PML is ruled out by complete clinical evaluation and appropriate diagnostic testing (see [Appendix 6](#)). A patient with confirmed PML should be withdrawn from the study. PML should be reported as a serious adverse event (with all available information) with immediate notification of the Medical Monitor.

Potential relapses should be recorded throughout the treatment period. Protocol-defined relapse is the occurrence of new or worsening neurological symptoms attributable to MS. Symptoms must persist for >24 hours and should not be attributable to confounding clinical factors (e.g., fever, infection, injury, adverse reactions to medications) and immediately preceded by a stable or improving neurological state for least 30 days. The new or worsening neurological symptoms must be accompanied by objective neurological worsening consistent with an increase of at least half a step on the EDSS scale, or 2 points on one of the appropriate FS scales, or 1 point on two or more of the appropriate FS scales. The change must affect the selected FS (i.e., pyramidal, ambulation, cerebellar, brainstem, sensory, or visual). Episodic spasms, sexual dysfunction, fatigue, mood change, or bladder or bowel urgency or incontinence will not suffice to establish a relapse. Sexual dysfunction and fatigue will not be scored. (Note: Adjudication of protocol-defined relapses will be performed by the Sponsor based on pre-specified criteria, applied to data collected by investigator, in a blinded fashion.)

For patients in the PPMS cohort, disease worsening or improvement over the treatment period will also be assessed and is defined as a 20% change in timed 25-foot walk test or a 20% change in 9-hole peg test time (see [Appendix 3](#)).

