2. STUDY DESIGN

This is an open-label, multicenter, biomarker study conducted at centers in multiple countries in which all eligible patients will be enrolled to a single treatment arm of ocrelizumab. The study will include an RMS cohort and a PPMS cohort. The RMS cohort is the main cohort and will include the majority of study participants. The RMS cohort will be comprised of four arms, three of which will have patients randomized into one of three arms (Arms 1-3) depending on the time of their second lumbar puncture (LP). In Arm 4, treatment with ocrelizumab will be delayed for 12 weeks after the first LP. The PPMS cohort will comprise a hypothesis-generating portion of the trial, as less is known about PPMS biomarkers.

The study treatment period is comprised of a Main Treatment Period and a Long-term Extension Period. For patients who complete the Main Treatment Period and continue to receive ocrelizumab, a Long-term Extension Period of the study will begin at Week 72 and administer ocrelizumab every 6 months for up to 4 years. The main treatment period will end on the earlier of the dates in which that patient received the Week 72 dose and the date in which Week 72 lab data were collected, or to data cutoff date or end of study date if patient hasn't received the week 72 dose. The long term extension period for each patient will start from the earliest day that patient takes the Week 72 dose or Week 72 lab data is collected till data cutoff date or end of study.

During the Main Treatment Period of the study, two LPs will be drawn from each patient. The two LPs will allow for assessment of biomarkers in CSF that are indicative of response to drug, pharmacokinetic/pharmacodynamic relationships, and/or disease pathogenesis in the CNS. Optional LPs may be collected upon patient's additional consent. Specifically:

Patients in the RMS cohort (Arms 1-3) will receive an LP before the start of dosing with ocrelizumab. Subsequently, these patients will be randomized into one of three arms for timing of the second LP, either Week 12, 24, or 52 following the first dose of ocrelizumab.

Patients in Arm 4 will receive two LPs, separated by a 12-week interval, before administration of the first dose of ocrelizumab. Patients in this arm will be asked if they are willing to give optional CSF samples via LP 12 weeks and 52 weeks after the ocrelizumab dose.

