2.3 DETERMINATION OF SAMPLE SIZE

The sample size calculations for this study are based on the assumed reduction from baseline in NfL at Weeks 24 and 52 combined (Arms 2 and 3) in the RMS cohort. Other biomarker measures are not considered for power determination.

Assuming (a) a 30% reduction from pre-treatment NfL (mean [SD] = 860 pg/mL [780 pg/mL]) to posttreatment NfL (mean [SD] = 602 pg/mL [310 pg/mL]) and a correlation coefficient of 0.6, resulting in an SD of 643 pg/mL for the change from pre- to post-treatment, and (b) a desired power of 80% with a Type 1 error of 5%, a sample size of 51 patients is required, with approximately 25 patients in Arm 2 and 26 patients in Arm 3.

This is the first study to explore the impact of ocrelizumab on CSF B-cell count. In a study by Piccio et al. (2010), the rate of undetectable B cells in CSF was 74% (21/26) after 24–30 weeks of rituximab as an add-on to immunomodulatory therapy. Based on this information and a sample size of 51 patients (Arm 2 and 3 combined), the expected 95% CI for the CSF Bcell undetectable rate will be: (0.61, 0.85).

In the RMS cohort, 15 patients will be included in Arm 1 to explore the possible reduction in NfL at Week 12 post-treatment and 15 patients will be assigned to the delayed start RMS control arm (Arm 4). At least 15 patients will be recruited to the PPMS cohort. The above sample sizes are not based on statistical considerations and are meant to help explore the changes in biomarkers and generate hypotheses for future studies.

Based on the above, the total sample size for this study will be at least 96 patients. The sample size will be increased by approximately 10% in order to account for potential missing post-treatment CSF information; therefore, the number of patients to be enrolled in the RMS cohort will be $N = 88$ (Arm 1: 16 patients, Arm 2: 28 patients, Arm 3: 28 patients, and Arm 4: 16 patients).

The PPMS cohort will enroll at least 16 patients, and additional PPMS patients were allowed to enroll to collect more information on biomarkers. The total sample size of the PPMS cohort may approximate 30 patients. Therefore, the total number of patients to be enrolled is at least 104, and may reach approximately 130 patients.

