4.4.2.3 Associations Among Biomarker Data

The following associations will be assessed separately for each arm at each scheduled visit:

- CSF with blood NfL, CD19+ B cells, and CD3+ T cells.
- change in CSF NfL levels, CD19+ B cells, CD3+ T cells with changes in T1 Gd-enhanced lesions from treatment baseline to post-baseline scheduled visits for arms 1-3 patients, and from pre-treatment baseline to treatment baseline visit for arm 4 patients.

- brain volume with CSF NfL levels.
- change in CSF NfL levels with new/enlarging T2 Gd-enhanced lesions.
- blood NfL with CSF CD19+B cells, CD3+T cells.
- blood NfL with T1 Gd-enhanced lesions.
- change in blood NfL with new and/or enlarging T2 lesions.

The Spearman's rank correlation coefficient will be used to evaluate the relationship among the levels of biomarkers or between levels of biomarkers and clinical parameters. Baseline values across patient arms may be pooled when appropriate. Scatterplots of the two-by-two associations may also be constructed to aid in the interpretation of the coefficients.

The following associations will be assessed by Mann-Whitney test:

- Baseline CSF NfL in DMT-experienced patients versus DMT-naïve patients.
- Baseline CSF NfL levels in patients with 0, 1 and >1 baseline T1 Gd-enhanced lesions.
- Percent change in CSF NfL in patients having at least one relapse event versus patients without relapse during the study.
- Percent change in CSF NfL in DMT-experienced patients versus DMT-naïve patients.

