4.9 SCOPE OF PLANNED ANALYSES

Interim Analysis 1 was limited to patients in the RMS cohorts Arms 1-3 who were enrolled by the CCOD. Biomarker analyses were limited to the Biomarker Population.

Interim Analysis 2 will be limited to patients in the RMS cohort Arms 1-4. Only data during the Main Treatment Period (defined in Section 2, before receiving Week 72 treatment) will be summarized at this interim analysis, which applies to patient disposition information, efficacy endpoints and safety endpoints.

The Final Analysis will include all patients (RMS cohort Arms 1-4 and PPMS cohort). Only data during the Main Treatment Period will be summarized.

The LTE Final Study Analysis will include all patients and all data collected during the Long Term Extension Period and the Safety Follow Up period.

The endpoints that will be included in each of the analyses and the analysis populations are specified in Table 2. Specific list of planned outputs will be available in SAP Module 2.

Table 2 Scope of Planned Analyses

Endpoint	Interim Analysis 1	Interim Analysis 2	Final Analysis	LTE Final Analysis
Disposition & Baseline Demographics, characteristics	X (RMS Enrolled Population, Biomarker Population)	X (RMS Enrolled Population)	X (Enrolled Population)	X (Enrolled Population)
Efficacy Endpoints (depend on data availability)	X (RMS Biomarker Population)	X Selected biomarkers as specified in SAP Module 2. (RMS Enrolled Population)	X (Enrolled Population, Per-Protocol Population)	X (Enrolled Population, Per-Protocol Population)
Pharmacokinetic (depend on data availability)	Not Planned	Depend on data availability	X (Pharmacokinetic Evaluable Population)	X (Pharmacokinetic Evaluable Population)
Exposure, AE, IRR	X (RMS Safety Population)	X (RMS Safety Population)	X (Safety Population)	X (Safety Population)
ADA	Not Planned	Not Planned	X (Safety Population)	X (Safety Population)
Vital Signs and General Laboratory Data	Not Planned	Not Planned	X (Safety Population)	X (Safety Population)

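### The relapse versus no-relapse split of the CSF changes counts relapses that occur after the CSF sample; it should count only those between the two LPs used for each change.

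*SAP*

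**What the plan says.** SAP 4.4.4 adds a descriptive split of the three primary CSF endpoints (NfL, CD19+ B cells, CD3+ T cells) "for patients who experienced at least one relapse during the study and patients experienced no relapse separately". SAP 4.4.2.3 lists, among the Mann-Whitney comparisons, "Percent change in CSF NfL in patients having at least one relapse event versus patients without relapse during the study". Neither line gives a relapse window, and neither says that only protocol-defined relapses count.

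In Arms 1-3 the scheduled CSF change ends at the second LP. SAP 2 sets the "timing of the second LP, either Week 12, 24, or 52 following the first dose of ocrelizumab".

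Relapse follow-up runs much longer. Protocol 4.5.6 states: "Potential relapses should be recorded throughout the treatment period". Under SAP 2, for patients who stay on drug, "a Long-term Extension Period of the study will begin at Week 72 and administer ocrelizumab every 6 months for up to 4 years". SAP 4.9 limits the data by analysis. For the Final Analysis, "Only data during the Main Treatment Period will be summarized", which means up to about Week 72. The LTE Final Analysis takes in "all data collected during the Long Term Extension Period and the Safety Follow Up period".

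**The concern.** The CSF change is fixed once the second sample is drawn, but relapse status keeps accumulating afterwards. An Arm 1 patient sampled at Week 12 who first relapses at Week 60 enters the relapse group, although the NfL change was measured while the patient was relapse-free.

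This has two consequences:

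- **Dilution.** If the question is whether relapse is reflected in CSF NfL, the relapse group includes patients whose relapse could not have affected the value analysed. A weak contrast could then be read as evidence that relapse does not affect NfL. Timing matters here because Protocol 1.1 describes NfL as a marker of acute neuronal injury that correlates with clinical relapses.
- **Dependence on cutoff.** The same patient, with the same two samples, can count as relapse-free at Interim Analysis 2 and as a relapser at a later analysis.

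The same SAP section does state the interval for the association between CSF change and Gd-enhancing lesions. The relapse line lacks an equivalent.

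**Working it through.** **The plan's own figures.** The documents give no expected number or timing of relapses for this study. The only sizing figure is 51 patients for the NfL change. It reproduces: SD = sqrt(780² + 310² − 2·0.6·780·310) = 643.7, and a paired t-test for a difference of 860 − 602 = 258 has power 0.794 at n = 50 and 0.802 at n = 51. The relapse split does not affect it.

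**Inputs.**

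- Patients per arm (SAP 2.3): "Arm 1: 16 patients, Arm 2: 28 patients, Arm 3: 28 patients, and Arm 4: 16 patients". Arms 1-3 give n = 16/28/28, 72 in total.
- Second LP at t = 12, 24 and 52 weeks (SAP 2).
- Follow-up H: Week 52 (last scheduled visit in protocol Version 4), Week 72 (end of the Main Treatment Period) and Week 240 (last extension visit in SAP Appendix 2).
- Annual relapse rate r, an assumption borrowed from the Phase II study in Protocol 1.2.1.2. On ocrelizumab 300 mg × 2 it was 0.125 (at Week 24), 0.086 (Weeks 24-48) and 0.186 (baseline to Week 72). On placebo it was 0.637, used as the upper end.

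**Formula.** Take the time to first relapse as exponential, with times in weeks. The share of the relapse group whose first relapse follows the second LP is

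Σ n·[exp(−rt/52) − exp(−rH/52)] / Σ n·[1 − exp(−rH/52)].

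**Worked case, r = 0.125, H = 72.**

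- exp(−0.125·72/52) = 0.8411, so 72 × 0.1589 = 11.4 patients relapse by Week 72.
- Before the second LP: 16 × (1 − 0.9716) + 28 × (1 − 0.9439) + 28 × (1 − 0.8825) = 0.45 + 1.57 + 3.29 = 5.3.
- Only after it: 11.4 − 5.3 = 6.1, or 54%.
- Arm 1: (0.9716 − 0.8411)/0.1589 = 82%.
- Arm 2: (0.9439 − 0.8411)/0.1589 = 65%.
- Arm 3: (0.8825 − 0.8411)/0.1589 = 26%.

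**Range, Arms 1-3 pooled.**

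| Annual rate | To Week 52 | To Week 72 | To Week 240 |
|---|---|---|---|
| 0.086 | 37% | 54% | 84% |
| 0.125 | 37% | 54% | 83% |
| 0.186 | 37% | 53% | 81% |
| 0.637 | 34% | 47% | 67% |

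The constant rate matters moderately. To Week 72, a rate falling from 0.125 to 0.086 after Week 24 gives 48%, and one rising from 0.086 to 0.186 after Week 24 gives 63%.

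**Size of the relapse group.** At an assumed 0.15 per year, 72 × (1 − 0.8125) = 13.5 patients relapse by Week 72. Before the second LP the count is 0.5 + 1.9 + 3.9 = 6.3.

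**The case against.** **Little rests on this.** SAP 4.4.4 is a descriptive summary, the only test is one Mann-Whitney line, and SAP 4 calls the analyses mostly descriptive and hypothesis-generating. This stands and limits the weight of the point. It does not make the grouping rule right.

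**Relapse may be meant as an outcome.** The objectives ask about correlation between biomarker change and efficacy measures, so a relapse after the sample could be of interest as something NfL change predicts. That is a fair question, but a different one. A split that mixes relapses before and after the sample answers neither.

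**There are later CSF samples.** The synopsis in the SAP offers an optional Week 52 LP to Arms 1, 2 and 4. The extension asks for further LPs, and SAP Appendix 2 windows CSF visits for all patients up to Week 240. Some later relapses therefore precede a measured change, so the shares above would be lower for later-visit changes. The SAP does not say which visit's change enters the relapse comparison. This objection stands, and it shapes the fix: the window must end at the sample used, not always at the second LP.

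**Stronger readings.** A reader might infer that about half the relapse group is misplaced whatever the analysis. That holds only for pooled Arms 1-3 followed to Week 72. A reader might also infer that the observed contrast is halved. That needs an effect that is constant whatever the gap between relapse and LP, and it is arithmetic on means, whereas the test uses ranks of percent change. Finally, a reader might infer that the comparison is confounded with arm. SAP 4.4 and 4.4.1 summarise by arm, and nothing says the relapse test is pooled. With common follow-up and a common rate, each arm also has the same chance of entering the relapse group, 1 − exp(−rH/52). What differs by arm is the dilution.

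**Unseen modules.** SAP Modules 2 and 3 may narrow the rule, but the SAP text refers to them for output lists and visit windows, not for a relapse window.

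**Conclusion.** The point holds. As written, both sections let relapses after the CSF sample define the relapse group, which dilutes the contrast and makes group membership depend on the data cutoff.

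The size depends mainly on follow-up, from about a third of the pooled relapse group at Week 52 to between two thirds and five sixths at Week 240. It also depends strongly on arm. These figures assume a constant relapse rate taken from another study, planned enrolment, LPs on schedule and no optional samples.

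The consequence is confined to one exploratory test and one descriptive summary. The primary summaries and the sample size are untouched. This is a cheap improvement.

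**What to change.** In SAP 4.4.2.3 and 4.4.4, define the relapse group separately for each CSF change: at least one protocol-defined relapse (Protocol 4.5.6) after the baseline LP and up to the post-baseline LP used for that change. State which post-baseline visit enters the Mann-Whitney test.

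Report relapses after that LP separately. If they are of interest, label that as the question of whether CSF change is associated with later relapse.

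Present the results by arm, or stratify the rank test by arm. With the window tied to the sample, longer intervals yield more relapses: at 0.15 per year, 3.9 of the 6.3 expected relapsers come from Arm 3.

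The cost is a few words and one derived flag. The second-LP study day is already derived in SAP 4.4 to assign the actual arm. The downside is a smaller relapse group, about 6 of 72 instead of 13 or 14 at 0.15 per year. That is too few for a firm conclusion, so the result should be labelled exploratory, with the number of relapsers shown in each arm.

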4.5 PHARMACOKINETIC AND PHARMACODYNAMIC ANALYSES

Details of pharmacokinetic and pharmacodynamics analyses will be described in a Modeling and Simulation Analysis Plan and results will be reported separately.

4.6 SAFETY ANALYSES

Safety analyses will be performed on the safety population. Summaries of adverse events will be generated by summarizing the incidence of treatment-emergent adverse events only. Treatment-emergent events are defined as those adverse events with observed or imputed onset date on or after the start date of study treatment. Only where the most extreme intensity is greater than the initial intensity will events with an onset date prior to the start of study treatment (and with an end date on or after the start of study treatment) be considered treatment emergent. An adverse event with a completely missing non-imputed start date will be assumed to be treatment emergent unless the adverse event has a complete non-imputed end date that is prior to start of study treatment. Protocol-defined relapses over the study period will also be summarized for the safety population.

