Statistical Methods

Statistical analyses will be performed on the analysis population, defined as all enrolled patients who received at least one infusion of ocrelizumab, even if the infusion was incomplete.

Primary Endpoints

Primary endpoints for the RMS cohort include:

- Change in levels of NfL in CSF from *treatment* baseline to post-treatment with ocrelizumab
- Change in number of CD19+ B cells in CSF from *treatment* baseline to post-treatment with ocrelizumab
- Change in number of CD3+ T cells in CSF from *treatment* baseline to post-treatment with ocrelizumab

Determination of Sample Size

The sample size calculations for this study are based on the assumed reduction from baseline in NfL (Gunnarsson et al. 2011) at Weeks 24 and 52 combined (Arms 2 and 3) in the RMS cohort. Other biomarker measures are not considered for power determination.

Assuming (a) a 30% reduction from *pre-treatment* NfL (mean [SD] = 860 pg/mL [780 pg/mL]) to post-treatment NfL (mean [SD] = 602 pg/mL [310 pg/mL]) and a correlation coefficient of 0.6, resulting in an SD of 643 pg/mL for the change from *pre-* to *post-treatment*, and (b) a desired power of 80% with a Type 1 error of 5%, a sample size of 51 patients is required, with approximately 25 patients in Arm 2 and 26 patients in Arm 3.

This is the first study to explore the impact of ocrelizumab on CSF B-cell count. In a study by Piccio et al. (2010), the rate of undetectable B cells in CSF was 74% (21/26) after 24–30 weeks of rituximab as an add-on to immunomodulatory therapy. Based on this information and a sample size of 51 patients (Arm 2 and 3 combined), the expected 95% CI for the CSF B-cell undetectable rate will be: (0.61, 0.85).

In the RMS cohort, 15 patients will be included in Arm 1 to explore the possible reduction in NfL at Week 12 post-treatment and 15 patients will be assigned to the delayed start RMS control arm (Arm 4). Fifteen patients will be recruited to the PPMS cohort. The above sample sizes are not based on statistical considerations and are meant to help explore the changes in biomarkers and generate hypotheses for future studies.

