2.5 SAFETY OBJECTIVES

The safety objective for this study is to evaluate the safety of ocrelizumab on the basis of the following endpoints:

- Nature, frequency, severity, and timing of adverse events

- Changes in vital signs, physical findings, and clinical laboratory results during and following ocrelizumab administration
- Adverse events related to biomarker sample collection

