2.2.5 Safety Outcome Measures

- Exposure to ocrelizumab, including information such as duration and dosage
- Incidence of
- Treatment emergent adverse events
- Serious treatment emergent adverse events

- Treatment emergent adverse events of special interest
- Treatment emergent adverse events leading to withdrawal of treatment
- Fatal adverse events
- Infusion-related reactions (IRR)
- Listing of lab abnormalities as needed

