4.1.4 Safety Population

Safety population is defined as all enrolled patients who received at least one infusion of ocrelizumab, even if the infusion was incomplete. Summary of safety outcome measures will be performed using the safety population. Patients will be summarized by the actual “arm” depending on when the patient actually received the 2nd LP.

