4.6.2 Adverse Events

Treatment emergent adverse events and serious treatment emergent adverse events will be coded, summarized overall and by NCI CTCAE v4.0 grade, and tabulated by body system and Preferred Term for individual events within each body system.

The number and percentage of patients with at least one IRR, and the intensity (highest grade for each patient) will be summarized in total and by dose cycle (patients with multiple events within an infusion will count only once). In addition, the total number of IRRs will be summarized (multiple events will be counted) in total and by dose cycle.

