4.6.5 Adverse Event of Special Interest (AESI)

All reported AESI will be summarized overall and by NCI CTCAE v4.0 grade, and tabulated by specific MedDRA bucket terms and preferred terms. The following types of events are of special interest:

- Drug-induced liver injury
- Suspected transmission of an infectious agent via product

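### The SAP text names no output for adverse events from biomarker sampling, a stated safety endpoint, and leaves out events from pre-dose lumbar punctures that start before the dosing date unless they worsen and persist

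*SAP*

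**What the plan says.** Protocol 2.5 gives three endpoints under the safety objective. The third is "Adverse events related to biomarker sample collection". The Version 5 synopsis in SAP Appendix 1 repeats it and extends the safety objective to the Long-Term Extension.

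SAP 4.6 sets the rule for all adverse event summaries: "Summaries of adverse events will be generated by summarizing the incidence of treatment-emergent adverse events only". An event is treatment-emergent if its onset date is on or after the date treatment starts. Earlier onset is admitted under a narrow condition: "Only where the most extreme intensity is greater than the initial intensity will events with an onset date prior to the start" of treatment count, and they must also end on or after that start. An event with a wholly missing start date counts unless a complete end date places it before treatment.

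SAP 4.6.2 carries the limit over to serious events: "Treatment emergent adverse events and serious treatment emergent adverse events will be coded, summarized overall and by NCI CTCAE v4.0 grade". The outcome measures in SAP 2.2.5 include items such as "Treatment emergent adverse events leading to withdrawal of treatment" and infusion-related reactions, but nothing on sampling. The special-interest list in SAP 4.6.5 has two types, drug-induced liver injury and "Suspected transmission of an infectious agent via product".

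On the population, SAP 4.1.4 reads: "Safety population is defined as all enrolled patients who received at least one infusion of ocrelizumab, even if the infusion was incomplete".

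**The concern.** This is a biomarker study that requires two LPs from every patient, and the protocol singles out sampling-related events as something to report. An endpoint with no named output can go unreported even when everyone follows the plan.

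Two separate gaps arise. First, events after post-dose LPs do reach the body-system and Preferred Term tables, but nothing there identifies them as related to sampling. Second, events from LPs done before the first dose are mostly governed by a rule built for drug exposure, not for a procedure that comes before the drug. An event that starts and resolves between the LP and the dose is not summarised at all. A patient who had an LP but was never infused is outside the safety population altogether.

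What is at stake is the description of procedural safety. No primary endpoint is touched.

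**Working it through.** **1. Endpoints against outputs.**

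| Safety endpoint (Protocol 2.5) | Place in the supplied SAP |
|---|---|
| Nature, frequency, severity and timing of events | 2.2.5, 4.6, 4.6.2, Table 2 |
| Vital signs, physical findings, laboratory results | 4.6.3, 4.6.6, Table 2 |
| Events from biomarker sampling | none found |

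**2. When an event from a pre-dose LP is summarised under SAP 4.6.** It must meet one of these conditions:

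- onset on or after the first-dose date (the rule works by date, so an event on the dosing day before the infusion is kept);
- earlier onset, worsening, and an end on or after treatment start;
- wholly missing start date and no complete end date before treatment.

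Any other event is left out.

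**3. Number of LPs.** Enrolment by arm is from SAP 2.3 and LP timing from SAP 2 and Protocol Table 1. The plan's own totals reproduce: 16 + 28 + 28 + 16 = 88 RMS patients, and 88 + 16 = 104.

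| Group | Patients | Mandatory LPs | Pre-dose | Post-dose |
|---|---|---|---|---|
| Arms 1-3 | 72 | 144 | 72 | 72 |
| Arm 4 | 16 | 32 | 32 | 0 |
| PPMS | 16 | 32 | 16 | 16 |
| Total | 104 | 208 | 120 | 88 |

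Pre-dose share: 120/208 = 57.7%. With about 30 PPMS patients (SAP 2.3) it is (72 + 32 + 30)/(2 × 118) = 134/236 = 56.8%. With 32 (Version 5 synopsis) it is 136/240 = 56.7%.

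The 120 split into 16 Arm 4 Week -12 LPs (16/208 = 7.7%) and 104 treatment-baseline LPs (104/208 = 50.0%).

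**4. Week -12 LPs.** Protocol Appendix 2 places these at Day -84 ± 7. An event starting at the LP must last about 84 ± 7, that is 77 to 91 days, and also worsen, to be counted. Loss is near-complete.

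**5. Treatment-baseline LPs.** In the Protocol Appendix 1 to 3 footnotes, the LP comes before the MRI, the MRI needs 2 business days of quality check before dosing, and both may precede the dose by up to 7 business days. With a fresh MRI the LP therefore falls 2 to 7 business days before the dose. In Arms 1-3 and PPMS, however, a screening MRI may serve as the baseline scan. That covers 72 + 16 = 88 of the 104 LPs, which can then fall on the dosing date, where same-day events are kept. For the 16 Arm 4 treatment-baseline LPs, the reuse footnote is attached to the Week -12 scan, so this route does not apply. Loss is partial, and its size cannot be derived.

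**6. Scheduled optional LPs.** All of these are post-dose, so they lower the pre-dose share. Full uptake is an assumption; the sources are SAP 2, the Version 5 synopsis and the CSF visit windows in SAP Appendix 2.

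- Arm 4 Week 12: 16. Week 52 in Arms 1, 2 and 4: 16 + 28 + 16 = 60. Together 76.
- Extension LPs at Weeks 144 and 240: 2 × 104 = 208.
- Main Treatment Period: 120/(208 + 76) = 42.3%.
- Whole study: 120/(208 + 76 + 208) = 120/492 = 24.4%.
- Half uptake of all 284 optional LPs: 120/(208 + 142) = 34.3%.

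Optional relapse LPs are not counted, as their number is unknown.

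**The case against.** The strongest reply is that the onset limit comes from the protocol. Protocol 6.5 tabulates events only from treatment on Day 1 onward. SAP 4.6 follows it and is slightly wider, because it adds worsening events and events without a start date. This stands. A reader might infer that the SAP narrowed what the protocol promised on onset; the documents do not support that. The gap is that neither text makes room for the protocol's own sampling endpoint.

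Collection limits what can be recovered. Before study drug, Protocol 5.3.1 and 5.4.2.1 call only for serious events caused by a protocol-mandated intervention. Protocol 5.2.1 does count pre-treatment LP events as adverse events, and the schedules tick adverse events at screening and Arm 4 Week -12, but a definition and a tick do not override a specific reporting rule. Non-serious pre-dose events may not be in the database.

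Module 2 may already hold the output, and SAP 2.2.5 is not exhaustive: it omits vital signs, which 4.6.6 covers. This also stands, so the finding is limited to the supplied text. If such an output exists and includes pre-dose events, it still needs a stated exception to the rule in 4.6.

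Protocol 6.5 lists all serious events, which would show serious pre-dose LP events. The SAP does not repeat that listing, and a listing of serious events does not by itself identify those due to sampling.

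On the population, a reader might infer that the SAP wrongly dropped patients with an LP but no infusion. The protocol synopsis agrees with the SAP: "Statistical analyses will be performed on the analysis population, defined as all enrolled patients who received at least one infusion of ocrelizumab". The Version 5 synopsis says the same. Only Section 6.4 of the Version 4 body adds patients with at least one LP, and the Version 5 body was not supplied.

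Finally, the objective is the safety of ocrelizumab, on which pre-dose events say little. That is true, but the protocol chose to list the sampling endpoint under that objective.

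**Conclusion.** The point holds as a minor one. A named safety endpoint has no named output in the supplied SAP text, and events from pre-dose LPs are summarised only under the three conditions in step 2 of the working. Loss is near-complete for the 16 Arm 4 Week -12 LPs. It is partial and unquantified for the 104 treatment-baseline LPs.

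A reader might take the 57.7% as the proportion of LP events that go unreported. The documents do not support that: it is a share of mandatory LPs, they give no data on event onset, and the share drops to 24.4% if every scheduled optional LP is done. Nor does it follow that the study can say nothing on LP safety. Events starting on or after the first-dose date, including those from the 88 mandatory post-dose LPs, are in the general tables; what they lack is attribution to sampling.

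The conclusion assumes that planned enrolment is met, that every mandatory LP is done, and that Module 2 contains no such output.

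**What to change.** In SAP 2.2.5 and 4.6, add one table or listing of adverse events related to LP or other biomarker sampling. If Module 2 already has one, name it there instead. It should:

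- cover all patients with at least one LP, regardless of onset relative to first dose, as a stated exception to the treatment-emergent rule and to the 4.1.4 population;
- identify events by the recorded relation to procedure if the eCRF holds it (the form was not supplied), or otherwise by a pre-specified term list and a time window after each LP date;
- report serious events for all LPs, and non-serious events mainly for post-dose LPs;
- make no comparison of pre-dose with post-dose rates, since capture is serious-only by rule before dosing and complete after it, so pre-dose LPs would look safer by construction;
- state that Protocol 5.3.1 and 5.4.2.1 limit pre-dose reporting to serious intervention-caused events, so non-serious pre-dose events may be under-captured.

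The cost is one output from data already recorded, plus a sentence in SAP 4.6. The drawback is incomplete capture of non-serious pre-dose events, which an SAP change cannot repair.
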